## **9.3 Characteristics of an Adverse Event**

Any adverse event, inclusive of all related study procedures, will be examined (section 9.1).

### **9.3.1 *Relationship to Study Intervention***

The causality, or attribution, of AEs refers to the relationship of the AE to the experimental intervention (drug/biologic). The investigator, using the following points, makes the assessment of whether there is a reasonable possibility of a causal relationship:

1. Related (Possible, Probable, Definite)
  - a. The event is known to occur with the study intervention.
  - b. There is a temporal relationship between the intervention and event onset.

- c. The event abates when the intervention is discontinued.
- d. The event reappears upon a re-challenge with the intervention.

2. Not Related (Unlikely, Not Related)

- a. There is no temporal relationship between the intervention and event onset.
- b. An alternate etiology has been established.

Based on the aforementioned points, the PI assigns attribution of the adverse event to the study treatment. Attribution categories are as follows:

- Definite: The AE is clearly related to the study treatment
- Probably: The AE is likely related to the study treatment
- Possible: The AE may be related to the study treatment
- Unlikely: The AE is doubtfully related to the study treatment
- Unrelated: The AE is clearly NOT related to the study treatment

### **9.3.2 *Expectedness of SAEs***

Expected events are those that have been previously identified as resulting from administration of the intervention. An adverse event is considered unexpected, for expedited reporting purposes only, when either the type of event or the severity of the event is **not** listed in:

- Current known adverse events listed in this protocol
- Drug package insert (for commercially available agent)

### **9.3.3 *Severity of Event***

This study will utilize version 5.0 of the CTCAE of the National Cancer Institute for toxicity and performance reporting. A copy of the CTCAE version 5.0 can be downloaded from the NCI website at:

[https://ctep.cancer.gov/protocolDevelopment/electronic\\_applications/docs/CTCAE\\_v5\\_Quick\\_Reference\\_5x7.pdf](https://ctep.cancer.gov/protocolDevelopment/electronic_applications/docs/CTCAE_v5_Quick_Reference_5x7.pdf).

## **9.4 *Reporting Procedures***

### **Procedures for Recording Adverse Events**

- AEs will be recorded from time of informed consent until 28 days post discontinuation of study drug or day of surgery, whichever is first.
- AEs will be recorded regardless of whether or not they are considered related to the study intervention.
- AEs will be recorded in the subject's medical record and in the research study records.

- All AEs considered related to study drug(s) or procedure will be followed until resolution to ≤ Grade 1 or baseline, deemed clinically insignificant, and/or until a new anti-cancer treatment starts, whichever occurs first.
- At the 3 month and 12 month follow up visits, any AEs deemed by treating physician or study PI to be probably related to the research blood draw procedure will be recorded at time of visit and followed until resolution to ≤ Grade 1 or baseline, deemed clinically insignificant.

### **Procedures for Recording and Reporting Serious Adverse Events**

- SAEs will be reported from time of informed consent until 28 days after discontinuation of cetuximab or definitive surgery, whichever is later.
- Any SAEs experienced after this 28-day period will only be reported if the investigator suspects a causal relationship (possibly, probably or definitely related) to the study treatment.
- SAEs will be reported on the SAE Submission Form and entered in SAE tab in OnCore within 1 business day of discovery of the event.
- SAEs include events related and unrelated to the study drug(s).
- SAEs will be recorded in the subject's medical record and on the appropriate study specific eCRF form within OnCore.
- All SAEs, regardless of relation to study drug, will be followed until resolution to ≤ Grade 1 or baseline and/or deemed clinically insignificant and/or until a new anti-cancer treatment starts, whichever occurs first.
- Recurrent episodes, complications, or progression of the initial SAE will be reported as follow-up to the original episode within 24 hours of the investigator receiving the follow-up information.

### **Expedited Reporting of Serious Adverse Events**

Depending on the nature, severity, and attribution of the serious adverse event an SAE report will be phoned in, submitted in writing, or both according to Table 1 below. All serious adverse events must also be reported to the UWCCC Data and Safety Monitoring Committee Chair. All serious adverse events must also be reported to the UW IRB (if applicable), and any sponsor/funding agency not already included in the list.

Determine the reporting time line for the SAE in question by using the following table.

**Table 1. Expedited Reporting Requirements for Adverse Events that Occur in Non-IND/IDE Studies Within 28 Days Post Surgical Intervention**

Reporting Requirements for Serious Adverse Events
--

**NOTE:** Investigators MUST immediately report to the *UWCCC DSMC, NIDCR (via Rho) and the IRB (if applicable)* ANY Serious Adverse Events, whether or not they are considered related to the investigational agent(s)/intervention. See below.

An adverse event is considered serious if it results in ANY of the following outcomes:

- 1) Death.
- 2) A life-threatening adverse event.
- 3) An adverse event that results in inpatient hospitalization or prolongation of existing hospitalization for  $\geq 24$  hours.
- 4) A persistent or significant incapacity or substantial disruption of the ability to conduct normal life functions.
- 5) A congenital anomaly/birth defect.
- 6) Important Medical Events (IME) that may not result in death, be life threatening, or require hospitalization may be considered serious when, based upon medical judgment, they may jeopardize the patient or subject and may require medical or surgical intervention to prevent one of the outcomes listed in this definition (FDA, ICH E2A and ICH E6).

**ALL SERIOUS adverse events that meet the above criteria\* MUST be immediately reported to the UWCCC within the timeframes detailed in the table below:**

Hospitalization	Grade 1 Timeframes	Grade 2 Timeframes	Grade 3 Timeframes	Grade 4 & 5 Timeframes
Resulting in hospitalization <math>\geq 24</math> hrs		10 Calendar Days		24-Hour; 5 Calendar Days
Not resulting in Hospitalization <math>\geq 24</math> hrs	Not required		10 Calendar Days	

*\*Hospitalization for planned surgical resection does not require reporting\**

**Expedited AE reporting timelines are defined as:**

- **24-Hour; 5 Calendar Days** – The AE must initially be reported within 24 hours of learning of the AE, followed by a complete expedited report within 5 calendar days of the initial 24-hour report.
- **10 Calendar Days** – A complete expedited report on the AE must be submitted within 10 calendar days of learning of the AE.

1

Serious adverse events that occur more than 28 days after the surgery and have an attribution of possibly, probably, or definitely related to cetuximab (or other research procedures such as biopsy or blood draws) require reporting as follows:

**Expedited 24-hour notification followed by complete report within 10 calendar days for:**

- All Grade 4, and 5 SAEs

**SAE Requiring [24] Hour Reporting Occurs at UWCCC**

**Report to the UWCCC DSMC:**

Reference the **SAE SOP** (Standard Operating Procedure) and the **SAE Reporting Workflow for DOTs** on the UWCCC website (<http://kb.wisc.edu/uwccc>) for specific instructions on how and what to report to the UWCCC for [24] hour initial and follow-up reports. **A follow-up report is required to be submitted within 5 days of the initial [24] hour report.**

For this protocol, the following UWCCC entities are required to be notified:

- a. [[contact]](mailto:[contact])
- b. UWCCC PIs: [name] and [name], PhD
- c. UWCCC PM: [name]
- d. Any other appropriate parties listed on the SAE Routing Form (for follow-up reports only)

**Report to the IRB**

Please refer to the document “Unanticipated Problems/Adverse Event Reporting Decision Guide” found on the UW Health Science IRB website:

<https://kb.wisc.edu/hsirbs/>. SAEs must be reported to the IRB Chair/director within 10 calendar days.

**SAE Requiring [10] Calendar Day Reporting Occurs at UWCCC**

**Report to the UWCCC DSMC:**

Reference the **SAE SOP** and the **SAE Reporting Workflow for DOTs** on the UWCCC website (<http://kb.wisc.edu/uwccc>) for specific instructions on how and what to report to the UWCCC for [10] calendar day reports.

For this protocol, the following entities are required to be notified:

- a. [[contact]](mailto:[contact])
- b. [UWCCC PIs: [name] and [name], PhD](mailto:UWCCC PIs: [name] and [name], PhD)
- c. [UWCCC PM: [name]](mailto:UWCCC PM: [name])
- d. [Any other appropriate parties listed on the SAE Routing Form \(for follow-up reports only\)](mailto:Any other appropriate parties listed on the SAE Routing Form (for follow-up reports only))

**Other Reportable Events**

Reporting timeframes begin when PI learns of the occurrence of the event.  
Refer to Table 2.

Table 2. Other Reportable Events Timeframe		
Event	Definition	Reporting
Breach of confidentiality	The exposure of any study information or communications directly related to a study subject to anyone not named as study staff or the release of a study subject's identifiable information to study staff who were not specified to receive such information in the protocol or IRB application.	Within 14 business days of knowledge of event
Protocol deviation	A deviation is an incident involving a departure from the IRB-approved protocol in the actual conduct of the study. Deviations may result from the action of the participant, investigator, or staff.	See details below
Major deviations	Deviations are considered major when the unapproved change(s) in previously approved research activities, implemented without IRB approval, may potentially adversely affect subjects' rights, safety, welfare, or willingness to continue participation, or affect the scientific design of the study and/or the integrity of the resultant data.	Within 14 business days of knowledge of event
Minor deviations	Deviations are considered minor when the unapproved change(s) in previously approved research activities, implemented without IRB approval, do not adversely affect subjects or the integrity of the study data.	Cumulative minor deviations are reported at the time of continuing review.

**Table 2. Other Reportable Events Timeframe**

Event	Definition	Reporting
Protocol violation	An incident involving an intentional deviation from the IRB-approved protocol that was not implemented in response to an emergency situation and that may impact a subject's rights, safety, and/or welfare, makes a substantial alteration to risks to subjects, or affects the scientific design of the study and/or the integrity of the resultant data. Violations may also be repeated deviations (major or minor) of the same nature. Violations can represent serious or continuing non-compliance with the federal regulations and guidelines for ethical conduct of human subject research.	Within 14 business days of knowledge of event
Protocol Exceptions	A protocol exception is an IRB-approved deviation for a single subject or a small group of subjects but is not a permanent revision to the research protocol.	Protocol exceptions must be approved by local IRB prior to implementation.

#### **9.4.1 *Unanticipated Problem Reporting to IRB and NIDCR***

Incidents or events that meet the OHRP criteria for unanticipated problems require the creation and completion of an unanticipated problem report form. OHRP recommends that investigators include the following information when reporting an adverse event, or any other incident, experience, or outcome as an unanticipated problem to the IRB:

- appropriate identifying information for the research protocol, such as the title, investigator's name, and the IRB project number;
- a detailed description of the adverse event, incident, experience, or outcome;
- an explanation of the basis for determining that the adverse event, incident, experience, or outcome represents an unanticipated problem;
- a description of any changes to the protocol or other corrective actions that have been taken or are proposed in response to the unanticipated problem.

To satisfy the requirement for prompt reporting, unanticipated problems will be reported using the following timeline:

- Unanticipated problems that are serious adverse events will be reported to the IRB and to NIDCR within 10 calendar days of the investigator becoming aware of the event.
- Any other unanticipated problem will be reported to the IRB and to NIDCR within 10 calendar days of the investigator becoming aware of the problem.
- All unanticipated problems should be reported to appropriate institutional officials (as required by an institution's written reporting procedures), the supporting agency head (or designee), and OHRP within one month of the IRB's receipt of the report of the problem from the investigator.

All unanticipated problems will be reported to NIDCR's centralized reporting system via Rho Product Safety:

- Product Safety Fax Line (US): [name]
- Product Safety Fax Line (International): [contact]
- Product Safety Email: rho\[contact]

General questions about SAE reporting can be directed to the Rho Product Safety Help Line (available 8:00AM – 5:00PM Eastern Time):

- US: [name]
- International: [contact]

#### **9.4.2 Serious Adverse Event Reporting to NIDCR**

Any AE meeting the specified Serious Adverse Event criteria will be submitted on an SAE form to NIDCR's centralized safety system via Rho Product Safety. This report may be sent by fax or email. Once submitted, Rho Product Safety will send a confirmation email to the investigator within 1 business day. The investigator should contact Rho Product Safety if this confirmation is not received. This process applies to both initial and follow-up SAE reports.

SAE Reporting Contact Information:

- Product Safety Fax Line (US): [name]
- Product Safety Fax Line (International): [contact]
- Product Safety Email: rho\[contact]

General questions about SAE reporting can be directed to the Rho Product Safety Help Line (available 8:00AM – 5:00PM Eastern Time):

- US: [name]
- International: [contact]

The study clinician will complete a Serious Adverse Event Form and submit via fax or email within the following timelines:

- All deaths and immediately life-threatening events, whether related or unrelated, will be recorded on the Serious Adverse Event Form and submitted to Product Safety within 24 hours of site awareness.
- Serious adverse events other than death and immediately life-threatening events, regardless of relationship, will be reported by fax within 10 calendar days of site awareness.

All SAEs will be followed until resolution or stabilization.

#### **9.4.3 *Reporting of SAEs and AEs to FDA***

Not applicable.

#### **9.4.4 *Events of Special Interest (if applicable)***

Not applicable.

#### **9.4.5 *Reporting of Pregnancy***

- Pregnancy will be reported from time of first study drug until 6 months after discontinuation of either study drug.
- Pregnancy will be reported to UW via an unanticipated problem submission and the NIDCR medical monitor within 1 business day of discovery of the event.

To ensure subject safety, each pregnancy in a subject on study treatment will be reported to UW and the NIDCR medical monitor within 1 business day of learning of its occurrence. The pregnancy will be followed to determine outcome, including spontaneous or voluntary termination, details of the birth, and the presence or absence of any birth defects, congenital abnormalities, or maternal and/or newborn complications.

### **9.5 *Halting Rules***

During the conduct of this study, subjects with adverse events and serious adverse events that are probably attributed to cetuximab will be evaluated and

analyzed weekly by the principal investigators. If >25% of subjects have serious adverse events that are probably related to pre-operative cetuximab treatment, then enrollment for the study will be suspended for further analysis.

Subsequent review of serious, unexpected, and related AEs will be evaluated by the DSMC, IRB, and the NIDCR. The NIDCR and local regulatory authorities retain the authority to suspend additional enrollment and administration of cetuximab for the entire study, as applicable.

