### Post-Surgical Assessment

Patients will be assessed for post-surgical complications (readmission, wound healing, infection) at 1 month +/- 2 weeks post-surgery. Complications will be categorized as related, probably related, possibility related, unlikely related, or unrelated to cetuximab.

Post-surgical adjuvant therapy will be delivered based on standard of care therapy as per recommendations of the University of Wisconsin Multidisciplinary Head and Neck Oncology Tumor Board. Receiving the two doses of cetuximab in the pre-operative setting will not be grounds for exclusion of cetuximab use at a later point. Such usages would include concurrent chemoradiotherapy, palliative combination chemotherapy and/or palliative monotherapy with cetuximab.

Distant metastatic disease and/or unresectable recurrent locoregional disease will be managed as per the institutional standard of care.

Expected duration of subject participation is approximately 13 to 16 months. The time to complete study enrollment is estimated to be 18 months. The time to complete the study analysis is estimated to be 30 months (from time of first patient enrolled to the time of last patient completed treatment).

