### **6.3 Modification of Study Product Administration for a Subject**

#### **Dose Delays/Dose Modifications**

- No dose modifications will be planned. Please refer to section 6.2.1 (subsection, Infusion Reactions) for more information regarding infusion rate decreases in the setting of infusion reaction.
- Dose delays secondary to intolerance (such as infusion reactions) are permitted. Subjects can be rechallenged with cetuximab within 3 days but will otherwise be discontinued from the study.
- Expected adverse events that would delay cetuximab infusion:
  - Grade 3 or higher nausea, vomiting, diarrhea, stomatitis, or rash uncontrolled despite maximal medical management due to a toxicity that is considered at least PROBABLY related to study treatment
  - Any other Grade 3 or higher non-hematologic toxicity, except grade 3 fatigue lasting >7 days, due to a toxicity that is considered at least PROBABLY related to study treatment
  - Grade 3 or 4 electrolyte abnormalities that are corrected within 48 hours will not be considered a serious adverse event.

---

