## **9.2 Time Period and Frequency for Event Assessment and Follow-Up**

Unanticipated problems will be recorded in the data collection system throughout the duration of the study.

All AE's will be recorded from the time of informed consent until 28 days past last dose of study drug or day of surgery, whichever is first. SAE's will be recorded from the time of informed consent through 28 days past last dose of study drug or 28 days post-surgery, whichever is later. Serious adverse events that occur more than 28 days after surgery and have an attribution of possibly, probably, or definitely related to cetuximab (or other research procedures such as biopsy or blood draws) require reporting per table 1.

At each study visit, the investigator will inquire about the occurrence of AE/SAEs since the last visit. Events will be followed for outcome information until resolution or stabilization.

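### Read literally, the 25% halting rule counts SAEs rated Probably related to cetuximab but not those rated Definite; the wording needs a short correction

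*Combined protocol and SAP*

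**What the plan says.** Section 9.5 (Halting Rules) has two sentences that matter here. The first sets the weekly review by the principal investigators, which covers "subjects with adverse events and serious adverse events that are probably attributed to cetuximab". The second sets the trigger: "If >25% of subjects have serious adverse events that are probably related to pre-operative cetuximab treatment", enrollment is suspended for further analysis.

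Section 9.3.1 gives the attribution scale: Definite, Probably, Possible, Unlikely, Unrelated. The top level reads "Definite: The AE is clearly related to the study treatment"; Probably is the next level down and means a likely relationship.

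Where the plan wants a cut-off that reaches the top of the scale, it usually says so. The dose-delay rules in section 6.3 use "at least PROBABLY related to study treatment". Section 9.2, on SAEs more than 28 days after surgery, covers those that "have an attribution of possibly, probably, or definitely related to cetuximab". The SAE reporting rules in section 9.4 list the same three levels.

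**The concern.** The halting rule names a single defined level of the scale, and that level is not the highest. Taken at its word, it leaves out the events for which the link to cetuximab is clearest. It is the only numeric trigger for toxicity across the study that I found in the plan, so its count should include those events. At stake is whether enrollment pauses when the true count has passed the limit but part of it is rated Definite. Nothing in the efficacy analysis depends on this.

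**Working it through.** **Inputs.** The threshold is strictly more than 25% of subjects (section 9.5). The attribution scale is the five levels in section 9.3.1. The planned size is 36 (section 5). The plan gives no derivation of the 25% figure, so there is no calculation of its own to reproduce. It also gives no expected SAE rate and no expected share of Definite ratings.

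**Step 1: compare the cut-offs.**

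| Place | Attribution named | Reaches Definite? |
|---|---|---|
| 6.3, dose delays | at least Probably | yes, by its wording |
| 9.2 and 9.4, late SAEs | possibly, probably, definitely | yes, by name |
| 9.5, weekly review | probably | not stated |
| 9.5, 25% trigger | probably | not stated |

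No sentence elsewhere says that the term in section 9.5 extends upward to Definite.

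**Step 2: when the two readings differ.** Let *n* be the number of subjects counted. Let *A* be the number with at least one SAE rated Probably or Definite. Let *D* be those among *A* who have a Definite SAE and none rated Probably.

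- Intended reading: pause if *A*/*n* > 0.25.
- Literal reading: pause if (*A* − *D*)/*n* > 0.25.
- The readings disagree exactly when *A* > 0.25*n* ≥ *A* − *D*.

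**Step 3: numbers.**

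- *n* = 12: 0.25 × 12 = 3, so at least 4 are needed. With *A* = 4 and *D* = 1, the intended reading gives 4/12 = 33.3% (pause). The literal reading gives (4 − 1)/12 = 3/12 = 25.0% (no pause).
- *n* = 36: 0.25 × 36 = 9, so at least 10 are needed. With *A* = 10 and *D* = 1, the intended reading gives 10/36 = 27.8% (pause). The literal reading gives 9/36 = 25.0% (no pause).
- Extreme case, *n* = 36 with *A* = *D* = 10: the intended reading gives 27.8% (pause), the literal reading 0/36 = 0% (no pause).
- *D* = 0: the readings agree at every *n*.

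These are counting examples, not forecasts. A probability of missing the pause would need an SAE rate, a Definite share and a schedule for computing the proportion. The documents give neither of the first two, and a weekly review does not fix the third, so I give no such probability.

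**The case against.** The best answer is that nobody would apply the rule this way. Section 9.4 uses the same bare phrase for adverse events "probably related to the research blood draw procedure" at the later follow-up visits, where leaving out definite cases would make no sense. The plan therefore does sometimes use *probably* as a floor, and a sensible team would count a clearly drug-caused SAE. This stands as evidence of intent. It does not remove the gap, because a stopping rule should not rely on readers setting aside a term the protocol has defined.

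The second answer is that other safeguards cover the case, and this largely stands. Table 1 in section 9.4 and section 9.4.2 send SAEs to the DSMC and NIDCR whatever their attribution. The rest of section 9.5 has the DSMC, the IRB and NIDCR review related events that are both serious and unexpected, and section 9.3.1 counts Definite as related. NIDCR and local authorities can suspend enrollment and dosing without reference to the 25% count. Section 10 lets the DSMC act on significant risk, and section 5.6 allows termination for unacceptable risk.

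For the same reasons, two stronger readings fail. A reader might infer that the plan chose to exclude Definite events. The inclusive wording in section 6.3 and the loose usage in section 9.4 point to a slip instead. A reader might also infer that a cluster of Definite SAEs could go unseen. The reporting and oversight provisions above do not support that.

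**Conclusion.** The rule is wrong as written, and the point is minor. Followed literally, section 9.5 undercounts by every subject whose only qualifying SAEs are rated Definite, and one such subject at the boundary is enough to prevent the pause (3/12 or 9/36). The conclusion rests on the text of sections 9.5 and 9.3.1 and on no assumed rate. If no subject falls in the Definite-only group, the wording makes no difference. Crossing the limit only suspends enrollment for further analysis, and no estimate, interval or test in section 12 is affected.

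Two extensions are tempting but not supported. One is that the denominator is the biopsied population. Section 12.2 uses that group to evaluate safety endpoints and does not link it to section 9.5, and treated patients are the natural base because only they can have a cetuximab-related SAE. The other is that the post-surgical scale in section 4 ("Complications will be categorized as related, probably related, possibility related, unlikely related, or unrelated to cetuximab") needs its top level equated with Definite. Section 9.3.1 already uses *related* to cover Possible, Probable and Definite, so that mapping would create a conflict.

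**What to change.** In both sentences of section 9.5, the weekly review and the 25% trigger, replace *probably* with *at least probably (Probable or Definite per section 9.3.1)*. This follows the form already used in section 6.3. The threshold and the action taken stay the same. The cost is a wording amendment to two sentences, with no new data, visits, patients or analyses. It can go into the next amendment.

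### Section 9.5 gives a cetuximab-related death no separate weight: beyond the first three treated subjects, a single such death does not by itself hold enrolment while it is reviewed

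*Combined protocol and SAP*

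**What the plan says.** The automatic rule is in Section 9.5 (Halting Rules). "If >25% of subjects have serious adverse events that are probably related to pre-operative cetuximab treatment", enrolment is suspended for further analysis. Death is one criterion in the general SAE definition (Section 9.1.3 and Table 1 of Section 9.4) and has no limb of its own in 9.5. The denominator of the 25% is not stated.

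Around that rule the protocol requires reporting and review:

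- Under 9.5, events probably attributed to cetuximab are evaluated and "analyzed weekly by the principal investigators".
- Section 9.5 continues: "Subsequent review of serious, unexpected, and related AEs will be evaluated by the DSMC, IRB, and the NIDCR".
- Section 9.4: "All serious adverse events must also be reported to the UWCCC Data and Safety Monitoring Committee Chair". Table 1 puts Grade 4 and 5 events on the fastest clock: "The AE must initially be reported within 24 hours of learning of the AE, followed by a complete expedited report within 5 calendar days". For the IRB: "SAEs must be reported to the IRB Chair/director within 10 calendar days".
- Section 9.4.2 sends every death, related or not, to NIDCR's safety system within 24 hours of site awareness.
- Section 10 has the DSMC review all SAEs that need expedited reporting.

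Every other route to suspension is a judgement. Section 9.5: "The NIDCR and local regulatory authorities retain the authority to suspend additional enrollment and administration of cetuximab for the entire study". Section 5.6 says the study may be suspended for reasonable cause, including unacceptable risk. Section 10 has the DSMC secure suspension once it finds significant risk. The rules in 6.2.1 for cardiopulmonary arrest, lung disease, infusion reaction and rash stop the drug for the individual only. Section 12.3 plans no interim analysis.

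**The concern.** A proportion rule suits SAEs that are expected at some background frequency. It suits a drug-related death poorly, because a single death can be reason enough to pause, and a proportion needs more and more events as the trial grows. Patients here are awaiting planned surgical resection, and Section 4 states that cetuximab before surgery is not standard of care. The practical question is whether a new patient can be enrolled and given a first dose after a related death and before its review is finished. Under the protocol text this is possible unless someone with authority decides otherwise. The protocol gives clocks for reporting but no turnaround for the DSMC's review.

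**Working it through.** **The rule.** Section 9.5 states no operating characteristics, so there is no figure of the plan's own to reproduce. With n subjects treated to date, the smallest count that exceeds 25% is floor(0.25n) + 1.

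| Subjects treated (n) | Subjects with a qualifying SAE needed | Check |
|---|---|---|
| 1–3 | 1 | 1/3 = 33.3%; 1/4 = 25% does not exceed 25% |
| 4–7 | 2 | 2/7 = 28.6%; 2/8 = 25% does not |
| 8–11 | 3 | 3/11 = 27.3%; 3/12 = 25% does not |
| 36 | 10 | 10/36 = 27.8%; 9/36 = 25% does not |

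So one related death trips the rule alone only at n = 1 to 3. Later it does so only if it pushes the running total of related SAEs past 25%. If the denominator were fixed at 36, even the early exception would disappear.

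**Chance of at least one related death.** The rates are assumptions: 0.5%, 1% and 2%. The documents give one point of context: 4/208 = 1.9% for arrest or sudden death with cetuximab plus radiotherapy (6.2.1). That is probably high for this trial, which gives two doses and excludes significant cardiac disease within 6 months (5.2). With 36 subjects, 1 − (1 − p)^36 = 16.5%, 30.4% and 51.7%.

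The share of first deaths that fall after subject 3 is (1 − p)^3 × [1 − (1 − p)^33] / [1 − (1 − p)^36] = 91%, 90% and 89%. When a related death occurs, it therefore usually comes where one death alone cannot trip the rule.

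**Enrolments during a review.** This is the quantity that measures the gap. Planned accrual is 36 patients in 18 months, or 2 a month, about 0.0657 a day. Assumed reviews of 7, 14 and 28 days span 0.0657 × 7 = 0.46, 0.92 and 1.84 enrolments. The expected number per trial is 36 × p × that figure:

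| Related-death rate p | 36p | 1 week | 2 weeks | 4 weeks |
|---|---|---|---|---|
| 0.5% | 0.18 | 0.08 | 0.17 | 0.33 |
| 1% | 0.36 | 0.17 | 0.33 | 0.66 |
| 2% | 0.72 | 0.33 | 0.66 | 1.3 |

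This slightly overstates the exposure. It ignores deaths in the first three subjects, which do suspend enrolment, and deaths late enough that accrual has finished. Multiplying by p again gives the expected further related deaths among those patients: 0.083 × 0.005 = 0.0004 up to 1.32 × 0.02 = 0.03 per trial.

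**The case against.** The strongest reply is that the protocol already handles this and that automatic against discretionary suspension is a matter of preference. Within a day of site awareness, a death reaches the safety system of NIDCR, which may stop enrolment and dosing for the whole study. The DSMC is told on the same clock, and the principal investigators review weekly. Investigators would probably pause anyway. The death rates are assumed, and the 2% comes from a different setting in which three of the four patients had prior coronary disease.

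Most of this stands, and it limits the size of the point. It does not remove it: a duty to report is not a hold, and the interval between report and completed review is left to discretion.

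The institutional procedures also stand as a limit. Section 9.4 refers to them "for specific instructions on how and what to report to the UWCCC for [24] hour initial and follow-up reports", and Sections 10 and 14.1 cite further monitoring documents. They were not available and might contain a default hold, so the point covers the protocol text only.

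Three stronger readings are tempting and are not supported:

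- A reader might infer that a related death could go unreviewed. Sections 9.4, 9.5 and 10 make review compulsory.
- A reader might infer that 9.5 never stops enrolment for a death. It does among the first three treated subjects, or when the death takes the total past 25%.
- A reader might run the numeric rule over the whole trial, counting deaths only, and find that all 36 enrol with at least one related death and no trip in 15%, 27% and 46% of trials at rates of 0.5%, 1% and 2%. Those figures describe the rule alone and assume that no oversight body acts, which contradicts the mandatory review. They also fall to 9%, 17% and 27% if a further 10% of subjects have non-fatal related SAEs. They should not carry the argument.

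**Conclusion.** The point holds in a limited form. The only automatic study-level trigger treats a related death like any other SAE, and after the third treated subject one such death does not suspend enrolment by itself. Reporting and review are prompt and compulsory, and suspension by judgement is available, but no protocol text holds enrolment by default while the review runs.

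The expected exposure is modest: about 0.08 to 1.3 patients per trial enrolled during a review, and about 0.33 at a 1% rate with a two-week review. This rests on assumed related-death rates of 0.5% to 2%, assumed reviews of 1 to 4 weeks, accrual at the planned pace, and subjects treated to date as the denominator. A true rate well above 2% would raise it. This is a cheap safety improvement worth making, not a fatal flaw.

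**What to change.** Add to Section 9.5:

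- Any death assessed as at least probably related to cetuximab suspends Step 2 enrolment and first cetuximab doses until the UWCCC DSMC has reviewed it.
- For subjects who have already had dose 1, the investigator decides promptly with the DSMC whether dose 2 is given.
- The >25% rule stays for other SAEs, with its denominator stated as subjects who have received cetuximab to date.

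An automatic hold on dose 2 is not proposed. It is due 7 ± 3 days after dose 1 (Section 7.2), and a subject who misses it is not evaluable for efficacy (Section 12.2). At planned accrual, 0.0657 × 4 to 10 days gives about 0.3 to 0.7 subjects between doses at any time, few enough to decide case by case.

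The cost is a few sentences, using the existing DSMC and 24-hour report, and a short accrual pause if the hold is used: about 0.5 to 1.8 patients per hold of 1 to 4 weeks. Because surgery is not delayed for the trial, some of them may miss their pre-surgical window. At qualifying-death rates of 0.5%, 1% and 2%, the chance of at least one hold is 17%, 30% and 52%.

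Widening the trigger to possibly related deaths would match the definition of related in 9.3.1. It is optional, since it would catch more peri-operative deaths.
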